6.2.1.3. Disease Control

Disease Control (DC) is defined as BOR of CR, PR, non-CR/non-PD or SD. DC rate (DCR) is the proportion of patients with DC.

DCR will be summarized by frequency counts and percentages.

6.2.1.4. Duration of Response

Duration of Response (DR) is defined, for patients with OR, as the time from the first documentation of objective response (CR or PR) to the date of first documentation of PD or death due to any cause. If a patient has not had an event (PD or death), DR is censored at the date of last adequate tumor assessment. The censoring rules for DR are as described for PFS in [Table 6](#).

$$\text{DR (months)} = [\text{date of event or censoring} - \text{first date of OR} + 1] / 30.4375$$

Kaplan-Meier estimates (product-limit estimates) will be presented by treatment group together with a summary of associated statistics including the median DR time with 2-sided 95% CIs. In particular, the DR rate at 2, 4, 6, 8, 12 and 16 months will be estimated with corresponding 2-sided 95% CIs. The CIs for the median will be calculated according to [Brookmeyer and Crowley](#) and the CIs for the survival function estimates at the time points defined above will be derived using the log-log transformation according to [Kalbfleisch and Prentice](#) (conftype=loglog default option in SAS Proc LIFETEST) with back transformation

to a CI on the untransformed scale. The estimate of the standard error will be computed using Greenwood’s formula.

DR will be displayed graphically and analyzed using Kaplan-Meier methodology. If the number of patients with OR is small, the Kaplan-Meier method may not provide reliable estimates. In this case, only descriptive statistics or listings will be provided.

6.2.1.5. Time to Response

Time to response (TTR) is defined, for patients with OR, as the time from the date of first dose of study treatment to the first documentation of objective response (CR or PR) which is subsequently confirmed.

$$\text{TTR (in months)} = [\text{first date of OR} - \text{date of first dose of study treatment} + 1] / 30.4375$$

TTR will be summarized using simple descriptive statistics (mean, SD, median, min, max, Q1, Q3).

6.2.1.6. Time to Progression

Time to progression (TTP) is defined as the time from the date of first dose of study treatment to the date of the first documentation of PD.

TTP data will be censored on the date the last adequate tumor assessment for patients without PD, for patients who start new anti-cancer therapy prior to PD (see [Section 5.2.6](#)), for patients who die without PD, or for patients with PD after 2 or more missing tumor assessments. Patients who do not have a baseline tumor assessment or who do not have any post-baseline tumor assessments will be censored on the date of first dose of study treatment.

The censoring and event date options to be considered for the TTP analysis are presented in Table 4.

$$\text{TTP (months)} = [\text{date of event or censoring} - \text{date of first dose of study treatment} + 1] / 30.4375$$

Table 4. TTP Outcome and Event Dates

Scenario	Date of event/censoring	Outcome
No adequate baseline assessment	Date of first dose of study treatment	Censored
PD 
 - After at most one missing or inadequate post-baseline tumor assessment, OR - ≤16 weeks after first dose of study treatment 	Date of PD	Event
PD after 2 or more missing or inadequate post-baseline tumor assessments	Date of last adequate tumor assessment ^a documenting no PD before new anti-cancer therapy is given or missed tumor assessments	Censored
No PD		Censored

Table 4. TTP Outcome and Event Dates

Scenario	Date of event/censoring	Outcome
Treatment discontinuation due to ‘Disease progression’ without documented progression	Not applicable	Information is ignored. Outcome is derived based on documented progression only.
New anti-cancer therapy given	Date of last adequate tumor assessment ^a documenting no PD before new anti-cancer therapy is given or missed tumor assessments	Censored
Death due to any cause		

^a. If there are no adequate post-baseline assessments prior to the PD, then the time without adequate assessment should be measured from the first dose of study treatment; if the criteria were met the censoring will be on the date of first dose of study treatment

Kaplan-Meier estimates (product-limit estimates) will be presented by treatment group together with a summary of associated statistics including the median TTP time with 2-sided 95% CIs. In particular, the TTP rate at 2, 4, 6, 8, 12 and 16 months will be estimated with corresponding 2-sided 95% CIs. The CIs for the median will be calculated according to Brookmeyer and Crowley and the CIs for the survival function estimates at the time points defined above will be derived using the log-log transformation according to Kalbfleisch and Prentice (conftype=loglog default option in SAS Proc LIFETEST) with back transformation to a CI on the untransformed scale. The estimate of the standard error will be computed using Greenwood’s formula.

Frequency (number and percentage) of patients with event and censoring reasons will be presented by treatment group. Reasons for censoring will be summarized according to the categories in Table 5 following the hierarchy shown.

Table 5. TTP Censoring Reasons and Hierarchy

Hierarchy	Condition	Censoring Reason
1	No adequate baseline assessment	No adequate baseline assessment
2	Start of new anti-cancer therapy before PD	Start of new anti-cancer therapy
3	Event after 2 or more missing or inadequate post-baseline tumor assessment/first dose of study treatment	Event after missing assessments ^a
4	Death without documented PD	Death for reasons other than PD
5	No PD and [withdrawal of consent date ≥ date of first dose of study treatment OR End of study (EOS) = Subject refused further follow-up]	Withdrawal of consent
6	No PD and lost to follow-up in any disposition page	Lost to follow-up
7	No PD and [EOS present OR disposition page for any epoch after screening says patient will not continue into any subsequent phase of the study] and no adequate post-baseline tumor assessment	No post-baseline tumor assessment
8	No PD and none of the conditions in the prior hierarchy are met	Ongoing without an event

^a. 2 or more missing or inadequate post-baseline tumor assessments.

The TTP time or censoring time and the reasons for censoring will also be presented in a patient listing.

Time of Follow-Up for TTP

A Kaplan-Meier plot for TTP follow-up duration will also be generated to assess the follow-up time in the treatment groups reversing the TTP censoring and event indicators. Kaplan-Meier estimates (product-limit estimates) will be presented by treatment group together with a summary of associated statistics including the median time of follow-up for TTP with 2-sided 95% CIs. In particular, the rate at 2, 4, 6, 8, 12 and 16 months will be estimated with corresponding 2-sided 95% CIs.

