5. GENERAL METHODOLOGY AND CONVENTIONS

5.1. Hypotheses and Decision Rules

5.1.1. Hypotheses and Sample Size Determination

There is no formal hypothesis testing planned for this study.

This study will enroll 20 patients to evaluate overall safety and tolerability with combination of avelumab plus axitinib. A sample size of 20 patients will provide at least 88% probability to observe at least one AE if the true incidence of the AE in the population is 10% or more.

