6.2.1.1. Objective Response

Best overall response (BOR) will be assessed based on reported overall lesion responses at different evaluation time points from the first dose of study treatment until the first documentation of PD, according to the following rules. Only tumor assessments performed on or before the start date of any further anti-cancer therapies will be considered in the assessment of BOR. Clinical deterioration will not be considered as documentation of disease progression.

BOR Based on Confirmed Responses:

- CR = at least two determinations of CR at least 4 weeks apart and before first documentation of PD.
- PR = at least two determinations of PR or better (PR followed by PR or PR followed by CR) at least 4 weeks apart and before first documentation of PD (and not qualifying for a CR).
- SD (applicable only to patients with measurable disease at baseline) = at least one SD assessment (or better) ≥ 8 weeks after first dose of study treatment and before first documentation of PD (and not qualifying for CR or PR).

- Non-CR/non-PD (applicable only to patients with non-measurable disease at baseline) = at least one non-CR/non-PD assessment (or better) ≥ 8 weeks after first dose of study treatment and before first documentation of PD (and not qualifying for CR or PR).
- PD = first documentation of PD ≤ 16 weeks after first dose of study treatment (and not qualifying for CR, PR, SD or non-CR/non-PD).
- NE: all other cases.

An objective status of PR or SD cannot follow one of CR. SD can follow PR only in the rare case that tumor increases by less than 20% from the nadir, but enough that a previously documented 30% decrease from baseline no longer holds. If this occurs, the sequence PR-SD-PR is considered a confirmed PR. A sequence of PR – SD – SD – PD would be a best response of SD if the window for SD definition has been met.

Objective Response (OR) is defined as confirmed BOR of CR or PR according to RECIST v1.1.

Patients who do not have a post-baseline radiographic tumor assessment due to early progression, who receive anti-cancer therapies other than the study treatments prior to reaching a CR or PR, or who die, progress, or drop out for any reason prior to reaching a CR or PR will be counted as non-responders in the assessment of OR. Each patient will have an objective response status (0: no OR; 1: OR). OR rate (ORR) is the proportion of patients with OR in the analysis set.

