6.6.2. Deaths

The frequency (number and percentage) of patients in the safety analysis set who died and who died within 30 days after last dose of study treatment as well as the reason for death, will be tabulated based on information from the ‘Notice of Death’ and ‘Survival Follow-Up’ eCRFs, by treatment group.

- All deaths;
- Deaths within 30 days after last dose of study treatment;

- Reason for Death:
 - Disease progression;
 - Study treatment toxicity;
 - AE not related to study treatment;
 - Unknown;
 - Other.

In addition, date and cause of death will be provided in individual patient data listing together with selected dosing information (study treatment received, date of first/last administration, dose) and will include the following information:

- AEs with fatal outcome (list preferred terms of AEs with outcome=Fatal, as well as AEs of Grade 5),
- Flag for death within 30 days of last dose of study treatment.

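### SAP Table 5 labels a death without documented PD as a death from another cause, which its condition does not establish and the recorded reason for death may contradict

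*SAP*

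**What the plan says.** SAP 6.2.1.6 defines TTP as "the time from the date of first dose of study treatment to the date of the first documentation of PD". Patients who die without PD are censored at the last adequate tumor assessment, or on the first-dose date if there is no post-baseline assessment. Protocol 9.2.1 has the same rule.

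Table 4 adds that stopping treatment for progression that was never documented is ignored: "Outcome is derived based on documented progression only". For best overall response, SAP 6.2.1.1 says: "Clinical deterioration will not be considered as documentation of disease progression".

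Table 5 assigns censoring reasons in a fixed order. Row 4 applies when a patient died and PD was not documented, and the reason it reports is "Death for reasons other than PD". These reasons go into a frequency table and a patient listing.

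SAP 6.6.2 counts deaths "as well as the reason for death, will be tabulated based on information from the" notice-of-death and survival follow-up pages. The categories are disease progression, study treatment toxicity, unrelated AE, unknown and other. Cause of death is also listed by patient.

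**The concern.** Lack of documented PD does not show that a patient died of something else. A patient can deteriorate, miss or be too ill for the next scan, and die of hepatocellular carcinoma with no radiological PD on file. The plan foresees patients of this kind: Table 4 has a row for undocumented progression, and the subjective-progression paragraph of Protocol Appendix 3 tells sites not to report such patients as PD.

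That patient would be listed under TTP as a death from another cause and under Deaths as a death from disease progression. SAP 6.2.1 analyzes tumor endpoints by investigator and by BICR, which opens a second route. A patient with PD by the investigator but not by BICR, who then dies without new therapy, would fall into row 4 of the BICR table.

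Readers use the censoring-reason table to judge whether censoring is related to the outcome. Here it would reassure them on a point that the plan has not checked. With 20 patients, one or two such deaths are a visible share of the table.

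**Working it through.** **1. The plan's own figure.** The only design calculation is in SAP 5.1.1: "A sample size of 20 patients will provide at least 88% probability to observe at least one AE". It takes 10% as the true AE rate. This gives 1 − 0.9^20 = 0.8784, which rounds to 88%. It has no bearing on TTP. The same section says: "There is no formal hypothesis testing planned for this study". No TTP assumption is stated.

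**2. Condition against label.**

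| Place | What it tests or reports |
|---|---|
| Table 5 row 4, condition | Patient died; PD not documented |
| Table 5 row 4, reason reported | Cause of death was not PD |
| SAP 6.6.2 | Recorded reason for death, with disease progression as a category |

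The condition holds for progression deaths and for other deaths, so the reported reason does not follow from it. Row 4 is reached only after rows 1 to 3. A patient with no adequate baseline, or with new anti-cancer therapy before PD, is reported under rows 1 or 2 and does not get this label.

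**3. Effect of the label on estimates.** None. It is applied after the event and censoring dates are set.

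**4. Possible effect of the censoring, closed form.** Assume a constant progression hazard h, with a fraction f of progressions surfacing only as death. The documents give no f. Documented PD then occurs at hazard (1 − f)h, and the median is ln 2 / [(1 − f)h]. The ratio to the median with all progressions counted is 1/(1 − f). The starting value of 4 months is the approximate sorafenib TTP in Protocol 1.2.1, not an assumption of this trial.

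| f | Ratio | 4 months becomes | Patients of 20, if all progress |
|---|---|---|---|
| 0 | 1.00 | 4.0 | 0 |
| 5% | 1.05 | 4.2 | 1 |
| 15% | 1.18 | 4.7 | 3 |
| 25% | 1.33 | 5.3 | 5 |

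**5. Simulation with scans.** Inputs: exponential progression with median 4 months, scans every 8 weeks (Protocol 7.6), cut-off at 18 months (SAP 2), n = 20, and 3,000 trials per f. Undocumented progressors die before the next scan. The SAP rule (censor at the last assessment) is compared with counting those deaths as events. Values are means over trials.

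| f | Median, SAP rule | Median, deaths as events | Difference (months) | 6-month proportion, SAP rule | 6-month proportion, deaths as events |
|---|---|---|---|---|---|
| 0 | 4.82 | 4.82 | 0 | 38.6% | 38.6% |
| 5% | 5.09 | 4.77 | 0.32 | 40.2% | 38.5% |
| 10% | 5.36 | 4.75 | 0.61 | 41.7% | 38.4% |
| 15% | 5.63 | 4.72 | 0.91 | 43.8% | 38.4% |
| 20% | 5.92 | 4.67 | 1.25 | 45.3% | 38.1% |

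At f = 15% the ratio is 5.63/4.72 = 1.19, close to the closed form. With f = 0 the mean median exceeds 4 because PD is dated at the next scan. In a very large sample (40,000 patients) the median stays at 5.52 months, the third scan, under both rules up to f = 20%. The 6-month proportion still moves, from 38.4% to 45.5% at f = 20%. The percentages for the median are therefore a guide to scale and not a prediction.

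**6. Against sampling error.** For an uncensored exponential with median 4 months and n = 20, the approximate standard error of the Kaplan-Meier median is 4/(ln 2 × √20) = 1.3 months. The shifts above do not exceed it.

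**The case against.** A reader might infer that the SAP overstates TTP. The documents do not support that. Censoring deaths without PD is the definition in Protocol 9.2.1 as well as in the SAP, so the estimate is too long only if one wants undocumented or fatal progression to count. Even then, it requires progression deaths without documented PD, and no count of these is given.

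The plan also limits such deaths. Protocol 7.6 calls for imaging when progression is suspected, and at withdrawal if none was done in the previous 8 weeks. Appendix 3 asks sites to try to document PD after treatment stops.

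A reader might also infer that these patients are kept in the analysis as though still at risk, or that the deaths are hidden. Neither is so. They leave the risk set at the last adequate assessment or on the first-dose date. PFS counts most of these deaths as events, OS is reported, and patient listings give both the censoring reason and the cause of death. TTP is a descriptive secondary endpoint with no decision rule.

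Finally, most patients with this cancer have cirrhosis (Protocol 1.2.1), so attributing death to tumor or to liver failure is uncertain. Investigator attribution would not belong in the BICR analysis.

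All of this stands against a claim of demonstrated bias, and the last point limits what a sensitivity analysis can show. None of it makes the row 4 label true. PFS is also not a complete safeguard: Table 6 censors deaths after new therapy, and deaths after two or more missing assessments unless they fall within 16 weeks of first dose.

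**Conclusion.** The labeling fault is certain on the face of the SAP. Followed as written, Table 5 can report a false reason for censoring, and SAP 6.6.2 can contradict it for the same patient. It affects the censoring-reason table and the listing, and no estimate.

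Whether TTP is lengthened is conditional. The direction is upward if some row 4 deaths are progression deaths, because the censoring is then informative. The size rests on an assumed f, a constant hazard and a borrowed 4-month median: zero at f = 0, and about 5% to 33% in the median for f of 5% to 25%. The plan should be corrected, but TTP as defined is not wrong.

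**What to change.** 1. In Table 5, rename the row 4 reason *Death without documented PD*.
2. Split the row 4 count by the reason recorded under SAP 6.6.2: disease progression, other (including toxicity and unrelated AE), or unknown.
3. Add one supplementary sensitivity analysis, for investigator-assessed TTP only, that counts deaths recorded as disease progression as events on the death date.
4. Leave the main TTP definition and the BICR analysis unchanged.

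The cost is a few lines in the SAP and one extra Kaplan-Meier run on data already collected. No protocol amendment is needed, since Protocol 9 and SAP 2 require one only for major changes to the primary endpoint or its analysis. The drawback is that item 3 relies on investigator-attributed cause of death, which is uncertain in patients with cirrhosis. It should be read as a check on informative censoring and not as a replacement estimate.

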6.2.1.7. Progression-free Survival

Progression-Free Survival (PFS) is defined as the time from date of first dose of study treatment to the date of the first documentation of PD or death due to any cause, whichever occurs first.

PFS data will be censored on the date of the last adequate tumor assessment for patients who do not have an event (PD or death), for patients who start a new anti-cancer therapy prior to an event (see [Section 5.2.6](#)) or for patients with an event after 2 or more missing tumor assessments. Patients who do not have an adequate baseline tumor assessment or who do not have an adequate post-baseline tumor assessment will be censored on the date of first dose of study treatment unless death occurred on or before the time of the second planned tumor assessment (ie, ≤ 16 weeks after date of first dose of study treatment) in which case the death will be considered an event.

The censoring and event date options to be considered for the PFS and DR analysis are presented in Table 6.

$$\text{PFS (months)} = [\text{date of event or censoring} - \text{date of first dose of study treatment} + 1] / 30.4375$$

Table 6. Outcome and event dates for PFS and DR analyses

Scenario	Date of event/censoring	Outcome
No adequate baseline assessment	date of first dose of study treatment ^a	Censored ^a
PD or death - After at most one missing or inadequate post-baseline tumor assessment, OR - ≤ 16 weeks after date of first dose of study treatment	Date of PD or death	Event
PD or death after 2 or more missing or inadequate post-baseline tumor assessments	Date of last adequate tumor assessment ^b documenting no PD before new anti-cancer therapy is given or missed tumor assessments	Censored
No PD and no death	Date of last adequate tumor assessment ^b documenting no PD before new anti-cancer therapy is given or missed tumor assessments	Censored

Scenario	Date of event/censoring	Outcome
Treatment discontinuation due to ‘Disease progression’ without documented progression	Not applicable	Information is ignored. Outcome is derived based on documented progression only
New anti-cancer therapy given	Date of last adequate tumor assessment ^b documenting no PD before new anti-cancer therapy is given or missed tumor assessments	Censored

^{a.} However if the patient dies ≤ 16 weeks after date of first dose of study treatment the death is an event with date on death date.

^{b.} If there are no adequate post-baseline assessments prior to PD or death, then the time without adequate assessment should be measured from the date of first dose of study treatment; if the criteria were met the censoring will be on the date of first dose of study treatment.

Kaplan-Meier estimates (product-limit estimates) will be presented by treatment group together with a summary of associated statistics including the median PFS time with 2-sided 95% CIs. In particular, the PFS rate at 2, 4, 6, 8, 12 and 16 months will be estimated with corresponding 2-sided 95% CIs. The CIs for the median will be calculated according to [Brookmeyer and Crowley](#) and the CIs for the survival function estimates at the time points defined above will be derived using the log-log transformation according to [Kalbfleisch and Prentice](#) (conftype=loglog default option in SAS Proc LIFETEST) with back transformation to a CI on the untransformed scale. The estimate of the standard error will be computed using Greenwood’s formula.

Frequency (number and percentage) of patients with each event type (PD or death) and censoring reasons will be presented by treatment group. Reasons for censoring will be summarized according to the categories in Table 7 following the hierarchy shown.

Table 7. PFS Censoring Reasons and Hierarchy

Hierarchy	Condition	Censoring Reason
1	No adequate baseline assessment	No adequate baseline assessment
2	Start of new anti-cancer therapy	Start of new anti-cancer therapy
3	Event after 2 or more missing or inadequate post-baseline tumor assessments/date of first dose of study treatment	Event after missing assessments ^a
4	No event and [withdrawal of consent date \geq date of first dose of study treatment OR End of study (EOS) = Subject refused further follow-up]	Withdrawal of consent
5	No event and lost to follow-up in any disposition page	Lost to follow-up
6	No event and [EOS present OR disposition page for any epoch after screening says patient will not continue into any subsequent phase of the study] and no adequate post-baseline tumor assessment	No adequate post-baseline tumor assessment
7	No event and none of the conditions in the prior hierarchy are met	Ongoing without an event

^{a.} 2 or more missing or inadequate post-baseline tumor assessments.

The PFS time or censoring time and the reasons for censoring will also be presented in a patient listing.

Time of Follow-Up for PFS

A plot will be generated to compare planned and actual relative day of tumor assessments by treatment group. A Kaplan-Meier plot for PFS follow-up duration will also be generated to assess the follow-up time in the treatment groups reversing the PFS censoring and event indicators. Kaplan-Meier estimates (product-limit estimates) will be presented by treatment group together with a summary of associated statistics including the median time of follow-up for PFS with 2-sided 95% CIs. In particular, the rate at 2, 4, 6, 8, 12 and 16 months will be estimated with corresponding 2-sided 95% CIs.

